#### Outcome Analysis

(a) Candesartan and cognitive/neuroimaging outcomes: General linear models will be used to compare the candesartan and lisinopril groups. Our main explanatory variable is the indicator for treatment group. Dependent variables will be the 12-month cognitive and neuroimaging measurements. For the cognitive analyses, our primary outcome is the executive function score derived using item response theory as outlined above in the EXAMINER methodology to account for education, age, and race influences on measures of executive abilities (developed by our collaborator, [name] team). For the cognitive outcome Mixed models with repeated measures (3 measurements) will be used. This procedure allows us to model the covariance structure to account for the potential variability across subjects in times of follow-up visits. Our main explanatory variable is the indicator for treatment group. The test of treatment effects on trial outcomes will be an interaction of treatment by visit (baseline,12 months follow-up). The main covariate adjustments will include history of prior stroke and prior exposure to ACEI/ARB. Additional covariate adjustments will be selected based on baseline statistically significant differences between the 2 randomized groups. The neuroimaging outcomes include measures of global perfusion, reactivity, FA, MD, and tractography metrics described above. **Table 3** provides a list of main variables. The multivariate models of the neuroimaging analysis will include the baseline values of the 12-month outcome variable, randomization stratification variables and other covariates that are significantly differ (at p<0.05) between the 2 groups at baseline. We will assess if the effects of randomized treatment are independent of blood pressure by comparing models with and without blood pressure change from baseline to 12 months. Summary statistics will include the model-adjusted mean and 95% confidence interval for each treatment group, and the mean (95% confidence interval) group difference on each 12-month outcome, as well as a p-value for group differences. All tests of significance on treatment group comparisons will use a two-sided alpha of 0.05.

(b) Role of vascular/inflammatory measures: Mediation analysis with bootstrapping will be used to identify the potential role of the vascular, endothelial and inflammatory markers on both our cognitive outcomes and neuroimaging outcomes. This method is particularly useful in clinical trials since it has superior statistical power for relatively small sample sizes. It also does not require a large effect size of the intervention on the outcome. The independent variable is treatment assignment. The dependent measures are executive function (EXAMINER score) and neuroimaging variables [perfusion, VR, VMR, FA, MD]. The potential mediators are [CIMT, stiffness (DIS, COMP), endothelial and measures (EPC, CRP, cytokines, VCAM, ICAM, MMP and PAI1)]. For each mediator, an estimation of the mediation effect will be calculated using the Freedman-Schatzkin difference in the regression coefficients ( $\beta_1 - \beta_2$ ) for the treatment effect obtained from the 2 regression models with and without the mediator: (outcome =  $\alpha + \beta_1 \times \text{treatment}$  and outcome =  $\alpha + \beta_2 \times \text{treatment} + \gamma \times \text{mediator}$ ). Bootstrapping method (5000 random samples) will be used to obtain the empiric distribution of the mediation effect and a mean, standard error and a confidence interval will be calculated. The null hypothesis for mediation is that the difference-in-coefficients ( $\beta_1 - \beta_2$ ) is zero.

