#### 10.4 Outcomes

Table 3 provides a list of main outcomes. Other Analyses' variables: Logical memory, digit span, DSST, WMH volume, regional brain measures

**Table 3:** Independent, primary and secondary outcomes and other variables to be used in the analyses

Independent:	Randomization Group (Candesartan vs Lisinopril)
Primary outcome:	Executive function (EXAMINER score)
Secondary Imaging outcomes:	Perfusion, CO2 VR, VMR, FA, MD, DTT t-scores, rs-fMRI
Mediators:	CIMT, stiffness, inflammatory markers, EPC
Tertiary outcomes:	memory, digit span, DSST, WMH volume, regional brain measures
Stratification variable:	Race, number of antihypertensive medications
Covariates:	Prior stroke and prior use of ACEI/ARB
Safety:	AE, SAE, incident dementia

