#### 10.5 Data Analysis

The 2 groups will be compared on baseline demographics, education level, physical function (SPPB), IADL, DEX, mood (CESD), cognitive and vascular/inflammatory measures and APO-E genotype. Also, baseline WMH, perfusion, VR, lacunar infarcts, and hippocampal volumes will be compared between the 2 groups using independent t-tests, nonparametric rank-based tests, or chi-square tests as appropriate. We will compare number of AE, SAE and incident dementia in the 2 groups as part of our safety analysis using Fisher's exact test; adverse event categories will utilize MedDRA (Medical Dictionary for Regulatory Activities) coding. To assess possible bias due to selective dropout, baseline comparisons between participants who complete vs. do not complete 12-month outcome assessments will be performed. To assess if equivalent blood pressure was achieved in both groups we will compare mean SBP and DBP in both groups during the follow-up visits. In addition, % controlled (defined as SBP<140 mm Hg/90 mm Hg) will be calculated for each visit post-titration. We will compare the % control in both groups using chi-square.

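### Covariates added to the neuroimaging models because they differ at p<0.05 at baseline leave the adjusted model unknown until the arms are compared; a list fixed in advance should replace the rule

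*Combined protocol and SAP*

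**What the plan says.** Section 10.5, Outcome Analysis (a), describes two kinds of model.

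- **Neuroimaging.** The models "will include the baseline values of the 12-month outcome variable, randomization stratification variables" and then "other covariates that are significantly differ (at p<0.05) between the 2 groups at baseline".
- **Cognitive.** "For the cognitive outcome Mixed models with repeated measures (3 measurements) will be used". Named covariates come first: "The main covariate adjustments will include history of prior stroke and prior exposure to ACEI/ARB". A selection rule follows, with no threshold in that sentence: "Additional covariate adjustments will be selected based on baseline statistically significant differences between the 2 randomized groups". The treatment test is described this way: "The test of treatment effects on trial outcomes will be an interaction of treatment by visit (baseline,12 months follow-up").

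Neither sentence lists the candidates. The opening paragraph of 10.5 compares the arms at baseline on demographics, education, SPPB, IADL, DEX, CESD, "cognitive and vascular/inflammatory measures and APO-E genotype", and on five imaging items (WMH, perfusion, VR, lacunar infarcts, hippocampal volumes). It leaves the choice among t, rank and chi-square tests to judgement.

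Table 3 in section 10.4, captioned "Independent, primary and secondary outcomes and other variables to be used in the analyses", gives prior stroke and prior ACEI/ARB use as the only covariates. The imaging sentence does not mention these two. No analysis restricted to prespecified covariates is planned.

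**The concern.** Section 10.2 randomizes in blocks within four strata. Apart from faults in conduct, any baseline difference beyond the strata is therefore chance. A baseline p-value measures how large that chance difference is. It does not say whether the variable predicts 12-month perfusion, FA or MD, and prediction is what makes adjustment worthwhile.

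Stating the rule in advance does not fix the model. The covariates depend on the realised imbalance, on which variables are counted within each family of measures, and on which test is applied to each. All of this is settled after the arms have been compared. Meanwhile, variables that do predict the outcome stay out of the model unless they happen to be imbalanced. At stake are the credibility of the adjusted imaging results as prespecified analyses, and some precision.

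**Working it through.** The plan attaches no figure to this rule, so there is none to reproduce. Its 80% power statement in section 10.6 plays no part here.

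**1. How often would a covariate be added?**
- Candidates: the baseline list in 10.5 has 11 single measures (education, SPPB, IADL, DEX, CESD, APOE, WMH, perfusion, VR, lacunar infarcts, hippocampal volumes) and 3 families (demographics, cognitive, vascular/inflammatory). Counting each family once gives 14. That this list is the candidate pool is an assumption.
- Expected number flagged: 14 × 0.05 = 0.70.
- At least one flagged, independent tests: 1 − 0.95^14 = 0.512.
- At least one flagged, assumed correlation of 0.3 among candidates (simulated): 0.44.
- For perfusion or reactivity the outcome's own baseline is already in the model, which leaves 13 candidates: 1 − 0.95^13 = 0.487.
- If the families are expanded, independent tests give 1 − 0.95^20 = 0.64 and 1 − 0.95^40 = 0.87. Correlation would lower these.

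**2. What does an added covariate do if it predicts nothing?** At N=140, a covariate just significant at baseline has t = 1.977, so its squared correlation with treatment is 1.977² / (1.977² + 138) = 0.028. The standard error of the treatment effect then grows by a factor of at least 1/√(1 − 0.028) = 1.014. In simulation the ratio given a flag was 1.027-1.029.

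**3. Rule versus fixed list (simulated ANCOVA, 10,000 trials per setting).** Inputs from the documents: N=140, 1:1 allocation in four strata, baseline correlation 0.4 (midpoint of 0.3-0.5 in 10.6), and effect sizes 0.41 (cerebral blood flow) and 0.24 (vasoreactivity). Assumed: blocks of 4, strata explaining 2%, and 14 candidates together explaining 0 or 10% of outcome variance, with mutual correlation 0 or 0.3. The fixed list is baseline value, two strata, prior stroke and prior ACEI/ARB use. The rule is that list plus flagged covariates.
- Type I error at N=140: rule 4.8-5.3%, fixed list 5.1-5.4%. With an assumed 100 scanned (section 4.2 enrols people who cannot have MRI), the rule gives 4.5-5.2%.
- Power at d=0.41, fixed/rule: 74.4/73.4, 75.2/74.3, 74.6/73.7, 74.9/75.1, 75.4/74.7, 74.2/74.2. Rule minus fixed runs from −1.0 to +0.2 points, with Monte Carlo error of about ±0.9.
- A separate 20,000-trial run (20 independent candidates, baseline correlation 0.5) showed no bias under either approach.

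**4. What would naming prognostic covariates gain?** As an analytic check, let three covariates explain 10% of outcome variance beyond baseline (assumed).
- Residual variance without them: 1 − 0.4² = 0.84. With them: 0.74.
- Non-centrality at d=0.41: 0.41 × √35 / √0.84 = 2.65, against 0.41 × √35 / √0.74 = 2.82.
- Power from the non-central t (133 and 130 df): 74.8% against 79.9%. At d=0.24 the same steps give 33.7% against 37.4%.

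The simulation agrees. Named covariates against the rule give 79.7 v 74.7 and 78.7 v 74.2 at d=0.41, and 36.9 v 33.1 and 36.2 v 33.5 at d=0.24. A further independent run gave 76-78% against 73-74% at d=0.41. If the covariates explain nothing there is no gain (73.3 v 73.4 and 74.5 v 74.3). The size depends on the inputs: the 20-candidate run at baseline correlation 0.5 gave 84.0 v 78.1.

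**The case against.** The strongest defence is that the rule is stated in advance, leaves the test valid and costs almost nothing. All of that stands. The power difference against the fixed list is about the size of simulation error.

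The rule can also help. When candidates explain 10% and are correlated at 0.3, root mean squared error in flagged trials at d=0.41 fell from 0.164 to 0.152 (14 prognostic covariates) and from 0.161 to 0.155 (three). It rose by about 2-3% only when the covariates predicted nothing. It would therefore be wrong to say that the rule brings no benefit.

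It is also fair that the sizeable gain comes from covariates that the documents do not name, with an explained variance that they do not give. The 14-candidate pool is likewise inferred.

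A reader might count how often the rule and a fixed list fall on different sides of p=0.05, and call that harm. It is only disagreement between two valid analyses. Adding fixed covariates, even ones that predict nothing, moves some p-values across the line too.

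A reader might also infer that the primary EXAMINER test is compromised, or that the cognitive model needs redesign. The documents do not support this. The named test is treatment by visit, and covariates entered only as main effects leave it unchanged with complete data. The plan does not say how they enter, and no explained variance is given from which to size an effect.

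What survives is that the rule is prespecified but the covariate set is not, and that imbalance is the wrong basis for choosing it.

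**Conclusion.** The point holds as a modest recommendation on the secondary imaging analyses, with a matching wording change for the cognitive model. The adjusted imaging model is not fixed before the arms are compared, and in about 44-51% of trials chance would add at least one covariate (14 candidates, correlation 0 to 0.3, both assumed). There is no bias and no type I inflation, and the rule's power cost against a fixed list is about 1 point or less. The avoidable loss is roughly 2-5 points of power at a baseline correlation of 0.4 if a few named covariates explain an assumed 10% of outcome variance, and none if they explain nothing. The case for change rests mainly on having a determinate model and on using prognostic information when it is known.

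**What to change.** Delete the baseline-significance rule from both models.

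- **Neuroimaging:** use one list fixed before unblinding. It should contain the outcome's baseline value, both stratification variables, and prior stroke and prior ACEI/ARB use (already the covariates in Table 3), plus any few baseline variables named now because they are expected to predict the outcome.
- **Cognitive model:** keep the covariates already named and drop the selection sentence.
- **Baseline comparisons:** report them descriptively. Any model adjusted for observed imbalance should be a labelled sensitivity analysis.

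The cost is SAP wording and one degree of freedom per single-parameter covariate: two for prior stroke and prior ACEI/ARB use, and one for each further variable. The present rule adds 0.7 on average with 14 candidates. No new data are needed. A named covariate that proves non-prognostic costs its degree of freedom and returns nothing, so the list should be short.

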## **6.2. Blood pressure measurement**

(1) Office blood pressure will be measured according to the American Heart Association guidelines: sitting position, rested for 5 minutes, appropriate cuff size (covering 60% of upper arm length and 80% of arm circumference), correct cuff placement (1-2 inches above brachial pulse on bare arm), and use of the bell of the stethoscope. Blood pressure will be measured in both arms. The arm with the higher blood pressure will be used throughout the study. We will obtain 2 seated followed by standing blood pressure measurements at 1 and 3 minutes during each visit.

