**7.2.3 Enrollment, Baseline, and Randomization:** During this phase, blood pressure measurements, detailed neuropsychological assessments, physical exam, brain MRI, and carotid ultrasound will be completed. Blood samples will also be collected for APOE, inflammatory and endothelial markers. Randomization and study intervention will occur after baseline data collection. Participants will then be started on the study medications. For all study related testing, the test results will not be disclosed to you unless deemed necessary by the study Physician.

**7.2.4 Follow-up Visits:** Following randomization, participants will be seen every two weeks, where antihypertensive study medications will be increased until they achieve blood pressure control (<140/90 mmHg), according to the designated trial protocol for blood pressure control. Blood pressure, heart rate, weight, adverse events (AE) and serious adverse events (SAE), pill count (to assess compliance), and use of non-study medications data will be collected. Once hypertension control is achieved, participants will be seen at 3, 6 and 12 months visits. Repeat neuropsychological assessment, blood draws (EPC and inflammatory markers), and urine collection will be conducted at the 6 and 12 months visit. Repeat neuroimaging and vascular ultrasound will be repeated at 12 months. BMP will also be checked at 2 weeks after randomization if only step one is needed, 4 weeks post randomization if treatment beyond step 1 is needed, and at 3, 6 and 12 months as shown in **Table 2**. Participants will also be contacted by phone as described in Table 2, Monthly during the follow-up phase. During these phone calls, participants will be asked about missing any doses in their medications and screened for any potential adverse events.

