### 8.3 Antihypertensive replacement protocol

Those with hypertension who are receiving antihypertensive medications will have their current medications tapered gradually using an established protocol that has minimal risk. Their primary care provider will also be notified, if the participant agrees, before initiating any changes in the participant’s blood pressure medications. If the subject agrees then a letter will be faxed or mailed to their primary care physician providing information about contacting the study personnel regarding any concerns or comments about the antihypertensive replacement. Participants will be provided with an automated blood pressure monitor and a blood pressure diary (Home Blood Pressure Monitoring Flow Sheet) to monitor their blood pressures at home. Contact by the study personnel will be weekly, or more if needed, for review of blood pressures. Once the participant is off all antihypertensive medications, he or she will undergo the baseline evaluation. The following protocol will be used for the withdrawal:

1- All participants will receive personalized written instructions on tapering and discontinuation of antihypertensive medications, description of symptoms associated with possible adverse events and familiarization with the study protocol (Home Blood Pressure Monitoring Flow Sheet). They will be instructed to share this information with their spouses or other members of their households. The timeline for medication tapering is summarized in the following table:

Number of antihypertensive meds	Week 1	Week 2	Week 3	Week 4
	Day 0-7	Day 8-14	Day 15-21	Day 22-28
One antihypertensive med	Half weekly dose	No meds Baseline Visit		
2 antihypertensive meds	Half weekly dose med 1 Full weekly dose med 2	No med 1 Half weekly dose med 2		
3 antihypertensive meds	Half weekly dose med 1 Full weekly dose med 2 and 3	No med 1 Half weekly dose med 2 Full weekly dose med 3	No med 1 and 2 Half weekly dose med 3	No Meds Baseline visit

2- Subjects and/or proxy will be provided with a portable automated blood pressure (BP) monitor and a diary to take home. They will be asked to measure BP 2x times a day (morning and before sleep) and record into a diary.

3-Daily/weekly dose reduction are shown in the Table above. Baseline visit will performed after all antihypertensive medications have been stopped.

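### Adding one baseline-to-12-month blood pressure change to the model cannot establish independence from blood pressure, and can leave a substantial part of a pressure-mediated effect labelled independent

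*Combined protocol and SAP*

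**What the plan says.** Outcome Analysis (a) in section 10.5 assesses independence from blood pressure by "comparing models with and without blood pressure change from baseline to 12 months". It does not say whether this means SBP, DBP or both, how much movement in the treatment coefficient would count, or whether baseline pressure enters as its own term.

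The two ends of the change score are measured in different states. Section 8.3 states: "Once the participant is off all antihypertensive medications, he or she will undergo the baseline evaluation". The 12-month reading is on treatment. Section 6.2 fixes the readings per visit: "We will obtain 2 seated followed by standing blood pressure measurements at 1 and 3 minutes during each visit". After titration, section 7.2.4 says "participants will be seen at 3, 6 and 12 months visits", and Table 2 has blood pressure taken at each. The 3- and 6-month pressures are not used in this model.

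The outcome models differ. For cognition, "For the cognitive outcome Mixed models with repeated measures (3 measurements) will be used", and "The test of treatment effects on trial outcomes will be an interaction of treatment by visit (baseline,12 months follow-up"). For imaging, "The multivariate models of the neuroimaging analysis will include the baseline values of the 12-month outcome variable", together with the stratification variables. Baseline blood pressure is not a listed covariate in either; it would enter only if the arms happened to differ significantly on it.

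Separately, section 10.5 compares "mean SBP and DBP in both groups during the follow-up visits" and the percentage controlled. Blood pressure is not among the mediators in Table 3 or in Outcome Analysis (b), so the bootstrap mediation analysis does not cover it.

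**The concern.** The rationale in sections 2.1 and 2.2 is that candesartan acts on the brain through selective AT1 blockade that leaves AT2 active, beyond lowering pressure. Within the outcome models, this comparison is the only analysis that separates the two explanations.

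Two features weaken it. First, adjusting for an error-prone stand-in for a mediator removes only part of the mediated effect, and what is left looks like a direct effect. The change score carries visit-to-visit noise from two visits as well as the spread of untreated baseline pressure. Second, the covariate is measured after randomisation, so causes shared by blood pressure and the outcome confound the adjusted coefficient. An unchanged coefficient could therefore be reported as support for the AT2 hypothesis when the effect runs through blood pressure.

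**Working it through.** The documents give no figure for this analysis, so there is none to reproduce. The check asks: if the treatment effect runs entirely through blood pressure, what share stays on the treatment coefficient after adjustment?

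**Inputs.** From the plan: the covariate, the drug-free baseline, the 3-, 6- and 12-month visits, and 70 per arm. Assumed, not in the documents: SD of long-run achieved pressure 10 mm Hg (variance 100); SD of true untreated baseline 15 (variance 225); correlation 0 between them; single-visit reliability ρ from 0.4 to 0.7; independent visit errors with the same variance at every visit, v² = 100(1 − ρ)/ρ.

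**Formula.** With one adjusting variable X and true driver M, the share left is 1 − cov(M, X)/var(X), taken within arm. Randomisation balances baseline pressure, so the arm difference in X equals that in achieved pressure and cancels. When baseline enters as its own term, the partial coefficient of the on-treatment term is used. At correlation 0 that coefficient is the on-treatment term's own reliability, whichever driver holds.

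- Change score, achieved pressure drives the outcome: 1 − 100/(325 + 2v²)
- Change score, true change drives the outcome: 1 − 325/(325 + 2v²)
- Month-12 reading plus baseline: 1 − 100/(100 + v²)
- Mean of months 3, 6 and 12 plus baseline: 1 − 100/(100 + v²/3)

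| ρ | v² | Change score, achieved drives | Change score, true change drives | Month 12 + baseline | Three-visit mean + baseline |
|---|---|---|---|---|---|
| 0.4 | 150 | 1 − 100/625 = 84% | 1 − 325/625 = 48% | 60% | 33% |
| 0.5 | 100 | 1 − 100/525 = 81% | 1 − 325/525 = 38% | 50% | 25% |
| 0.6 | 66.7 | 1 − 100/458.3 = 78% | 1 − 325/458.3 = 29% | 40% | 18% |
| 0.7 | 42.9 | 1 − 100/410.7 = 76% | 1 − 325/410.7 = 21% | 30% | 12.5% |

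If true change is the driver, splitting a single reading into two terms does worse than the change score (30–60% against 21–48%). The gain that holds under both drivers comes from the three-visit mean combined with baseline. Allowing correlations up to 0.5, that model leaves 12–37% (achieved drives) or 12–59% (change drives), against 76–95% and 21–63% for the change score.

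**Wider grid.** 144 combinations: achieved SD 6–12, visit SD 6–12, baseline SD 10–20 mm Hg, correlation 0–0.5.

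| Model | Range | Median |
|---|---|---|
| Change score, achieved drives | 54–106% | 89% |
| Change score, true change drives | 12–79% (above half in 28% of cells) | 40% |
| Month 12 + baseline, achieved drives | 20–83% | 52% |
| Three-visit mean + baseline, achieved drives | 8–62% | 26% |

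**Confounding.** In a large simulation (achieved SD 8, baseline SD 15, visit SD 8, correlation 0.4), an unmeasured cause of both pressure and outcome moved the share for month 12 plus baseline from 53% to anywhere between 26% and 69%, depending on its sign and strength.

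**Mixed model.** Let b be the coefficient of the change score entered as a main effect, and d the arm difference in it. With complete data, the treatment coefficient at every visit shifts by the same b × d, so the difference between month 12 and baseline is unchanged. One simulated data set of 140 shows this: the interaction is 0.1282 with and without the covariate, and 0.1002 once change-by-visit terms are added.

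**The case against.** The best defence is the design. Misattribution needs an arm difference in blood pressure, and both arms are titrated to the same target of below 140/90 mm Hg with open-label add-ons (sections 3 and 5.3). Section 10.5 also compares achieved pressure between arms across follow-up. This stands in part: it caps how large a pressure-mediated effect could be. It does not settle the matter. The comparison has no equivalence margin, and with 70 per arm and an assumed SD of 10, 13 or 16 mm Hg its power is 43%, 28% or 20% for a 3 mm Hg difference and 84%, 62% or 46% for 5 mm Hg.

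A reader might infer something stronger: that the planned adjustment would label most of a purely pressure-mediated effect as independent, and so leans towards the AT2 conclusion. The documents do not support that. They give no variance, reliability or arm difference for blood pressure. The 76–84% range needs achieved pressure, not change, to be the driver. Confounding can push either way, and the plan sets no decision threshold that could lean.

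Two smaller objections also stand. Contrasting the change score alone with a three-visit mean plus baseline alters two things at once: at reliability 0.7 with achieved pressure as driver, the baseline term takes the share from 76% to 30%, and the extra visits from 30% to 12.5%. And this is a supportive analysis; several sensible covariates (prior stroke, prior ACEI/ARB use, stratification variables) are already planned.

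**Conclusion.** The concern holds in a conditional form. The planned comparison can leave a substantial, sometimes major, part of a pressure-mediated effect labelled independent of blood pressure, and an unchanged coefficient would not establish independence. The share is 76–84% or 21–48% under the stated assumptions, according to whether achieved pressure or true change drives the outcome. It is not a fixed property of the plan.

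The firmest part needs no variance assumption: for the EXAMINER score, a change score entered only as a main effect makes the check uninformative when data are complete, and the plan does not specify the interaction that would avoid this. The common target and the arm comparison limit the problem without removing it. The randomised comparison and its p-value are untouched.

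**What to change.** In Outcome Analysis (a), for this supportive analysis only:

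- Replace the change score with each participant's mean SBP and mean DBP over the 3-, 6- and 12-month visits. Enter baseline pressure and the planned baseline covariates (prior stroke, prior ACEI/ARB use, race, number of antihypertensives) as separate terms.
- In the mixed model for the EXAMINER score, include the blood-pressure-by-visit term and report the treatment-by-visit estimate with and without it.
- Add a sensitivity analysis over assumed reliability of the pressure measure, for example single-visit values from 0.4 to 0.7.
- Label the result exploratory. State that an unchanged treatment coefficient does not establish independence from blood pressure, because of measurement error and possible pressure–outcome confounding.

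The change reduces the error without removing it: 12.5–33% still remains under the assumptions above, which is why the labelling matters as much as the covariate. The cost is SAP wording and a little code on data already collected. The downside is a more cautious claim about mechanism.

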## 1. STUDY OBJECTIVES

Our overall aim is to conduct a 1-year double blind randomized control trial comparing candesartan to lisinopril in 140 individuals with hypertension and executive mild cognitive impairment. Our specific aims are:

**Aim 1:** Investigate the effect of candesartan compared to lisinopril on the progression of cognitive function evaluated by a battery of neuropsychological tests assessing executive function, memory, attention and cognitive speed in hypertensive older adults with executive mild cognitive impairment.

**Hypothesis 1:** Candesartan is associated with less decline in executive function compared to lisinopril.

**Aim 2:** Investigate the effect of candesartan compared to lisinopril on cerebral perfusion, cerebrovascular reserve (vasoreactivity to carbon dioxide) assessed by arterial spin labeling MRI and microvascular brain injury reflected by diffusion tensor imaging measures of connectivity.

**Hypothesis 2:** Candesartan is associated with less decline in cerebral perfusion, vasoreactivity to carbon dioxide, and evidence of microvascular brain injury (white matter integrity) compared to lisinopril.

**Aim 3:** Identify underlying mechanisms explaining the effects of candesartan on neuroimaging (AIM 3A) and cognitive (AIM 3B) outcomes relative to lisinopril including effects on arterial stiffness, atherosclerosis (carotid intima-media thickness, CIMT), and vascular inflammatory and endothelial markers.

**Hypotheses 3:** Relative to lisinopril, treatment with candesartan is associated with lower CIMT, arterial stiffness, and inflammatory and endothelial function markers at 12 months, which in turn are associated with improved cerebral perfusion, vasoreactivity, and white matter integrity measures (Hypotheses 3A) as well as less decline in executive function (Hypotheses 3B) at 12 months.

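### For EXAMINER, section 10.5 tests the difference in change but promises an estimate and confidence interval only for the 12-month difference, with a p-value tied to neither

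*Combined protocol and SAP*

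**What the plan says.** Section 10.4 (Table 3) gives the primary outcome as "Executive function (EXAMINER score"). Hypothesis 1 in section 1 is about change: "Candesartan is associated with less decline in executive function compared to lisinopril".

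The analysis is in 10.5, Outcome Analysis (a). In order, that paragraph says:

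- General linear models are introduced first, with "Dependent variables will be the 12-month cognitive and neuroimaging measurements".
- It then changes method: "For the cognitive outcome Mixed models with repeated measures (3 measurements) will be used". Table 2 schedules neuropsychological testing at baseline, 6 and 12 months, so the three measurements include baseline.
- The test is named: "The test of treatment effects on trial outcomes will be an interaction of treatment by visit (baseline,12 months follow-up").
- On covariates: "The main covariate adjustments will include history of prior stroke and prior exposure to ACEI/ARB". The baseline score is not listed.
- Baseline adjustment is stated for imaging only: "The multivariate models of the neuroimaging analysis will include the baseline values of the 12-month outcome variable".
- The results to be reported, for all outcomes, are adjusted means by arm and "the mean (95% confidence interval) group difference on each 12-month outcome, as well as a p-value for group differences".

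No estimate or interval is promised for the difference in change. No sentence links the promised p-value to the interaction or to the 12-month difference.

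**The concern.** In the cognitive model as written, the tested contrast is candesartan's change from baseline to 12 months minus lisinopril's. The reported contrast is the gap between arms at 12 months. Nothing in the model forces the arms to share a baseline mean, so the second equals the first plus the observed baseline gap.

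The primary result would therefore carry an interval for one contrast and a significance test of another. A reader could meet a 12-month interval that includes zero beside a significant interaction, or the reverse, and the plan does not say how to report that.

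**Working it through.** **Inputs**
- 70 completers per arm (Sample Size and Population), 1:1 allocation (10.2), two-sided alpha 0.05 (10.5).
- Correlation r of baseline with 1 year: 0.3 to 0.5 (10.6). The measure it came from is not named.
- Effects (10.6): 0.48 SD is the pilot effect for TMT-B, the only cognitive one. 0.24 is the stated detectable effect. The pilot value of 0.41 is for cerebral blood flow, an imaging outcome, and is not used.
- Assumed: complete data, and the same between-person SD at baseline and 12 months. Effects are in units of that SD.

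**The plan's own figure**

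Section 10.6 states 80% power for 0.24 with 140 participants. It reproduces as a two-measurement repeated-measures interaction with f = 0.24/2 = 0.12 and r = 0.5: noncentrality = f²Nm/(1 − r) = 0.0144 × 140 × 2/0.5 = 8.06, power 80.5% (66% at r = 0.3). Since (0.48/0.169)² = 8.06, this is the same as a 0.48 SD difference in change. Read as a standardised 12-month difference, 0.24 has 29% power. How 0.24 is meant is a separate matter; results are given for both values.

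**How far apart the contrasts can be**

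12-month difference = difference in change + baseline difference.
- SE of the baseline difference = √(2/70) = 0.169 SD, so its 95% range is ±0.33 SD.
- SE of the 12-month difference = √(2/70) = 0.169 SD.
- SE of the difference in change = √(2(1 − r) × 2/70) = 0.200 SD (r = 0.3) or 0.169 SD (r = 0.5).
- Correlation of the two estimates = √((1 − r)/2) = 0.59 (r = 0.3) or 0.50 (r = 0.5).

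**How often exactly one is significant** (simulated from that joint normal distribution, cut-off 1.96)

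| True effect | r = 0.3 | r = 0.5 |
|---|---|---|
| 0.48 SD | 26% | 22% |
| 0.24 SD | 24.5% | 28.5% |
| 0 | 7.6% | 8.1% |

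One contrast being significant while the other points the opposite way occurs in under 1% of trials at all three effects.

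**Two illustrations, r = 0.5**
- Baseline difference 0.15, 12-month difference 0.40: the 12-month CI is 0.40 ± 0.33 = 0.07 to 0.73. The interaction is 0.40 − 0.15 = 0.25, p = 0.14.
- Baseline difference −0.15, 12-month difference 0.25: the 12-month CI is −0.08 to 0.58. The interaction is 0.25 + 0.15 = 0.40, p = 0.018.

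**Sensitivity to r**

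Section 6.3 gives EXAMINER a test-retest reliability above 0.9, so its one-year correlation may exceed 0.5. At an assumed 0.7, exactly one contrast is significant in 37% of trials at 0.24 and 19% at 0.48. At 0.9 the figures are 63% and 19%. A significant result with the other contrast pointing the opposite way then reaches about 1.7% (r = 0.7) or 6% (r = 0.9) at worst. A higher correlation does not remove the problem.

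**The case against.** Four points can be made for the plan.

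- A reader might infer that the plan prints the interaction p-value beside the 12-month interval. The text does not say so. Estimate, interval and p-value sit in one clause about group differences, and the natural reading is that they belong together. This stands. But the primary outcome then has a second p-value besides that of the named test, and the plan does not connect the two.
- The named test fixes the significance decision, so a claim of inflated type I error is not supported. Under no effect, at least one of the two contrasts is significant in about 9% of trials, but that is an error rate only if the analyst may choose. This also stands; what remains is that the promised interval does not describe the tested contrast.
- Randomisation gives both contrasts the same expected value, so they are two estimators of one treatment effect, and most disagreements are two moderately powered tests falling either side of 1.96. This stands, and the low rate of opposite directions supports it. It does not help the reader of a single trial, where the baseline gap has one realised value.
- The reported means are to be model-adjusted, and covariates that differ significantly at baseline are to be added. For the cognitive model the named covariates omit the baseline score, and a significance rule would catch only baseline gaps beyond about 0.33 SD. This does not close the gap.

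**Conclusion.** The point holds as an unlinked test and estimate for the primary outcome. Followed exactly, 10.5 gives a test of the difference in change, an interval for the 12-month difference, and a p-value whose contrast is not stated. At 70 per arm the two contrasts differ by a baseline gap with SE 0.17 SD, which is 35% of the 0.48 effect (0.169/0.48) and 70% of the 0.24 effect (0.169/0.24). The disagreement rates rest on complete data, equal SDs, and r of 0.3 to 0.5 applying to EXAMINER.

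It does not extend to the imaging outcomes, where the 12-month value is modelled with baseline as a covariate. Nor do the documents support saying that the two contrasts target different treatment effects. It should be corrected because it concerns the headline result, and the correction is small.

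**What to change.** State in 10.5 that for EXAMINER, and for any other outcome analysed by the mixed model, the estimate, 95% CI and p-value all come from one pre-specified contrast in one model. Either choice is coherent:

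- **Between-arm difference in 12-month change.** This is the interaction already named as the test, and it matches Hypothesis 1. The 95% half-width is 1.96 × 0.200 = 0.39 SD (r = 0.3) or 1.96 × 0.169 = 0.33 SD (r = 0.5).
- **Common-baseline or baseline-adjusted 12-month difference, used for both test and estimate.** The half-width is 1.96 × 0.169 × √(1 − r²) = 0.32 SD (r = 0.3) or 0.29 SD (r = 0.5). Power at 0.48 SD is about 85–91%, against 67–81% for change.

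The second is more precise but replaces the named test, so it should be fixed before any unblinded look. Show unadjusted 12-month means by arm as description only, and bring the sentence naming 12-month values as the dependent variables into line with the choice. The cost is a short edit to 10.5, with no new data and no added participants. The first option leaves power as it is under the current test; the second raises it.
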